5.2 PARTICIPANT EXCLUSION CRITERIA

- 1) Chronic renal dysfunction, including ESRD or eGFR < 20ml/min/1.73m².
- 2) Shock of any kind. Any requirement for vasopressors or inotropes.
- 3) SBP < 120
- 4) Need for immediate intubation
- 5) Acute Coronary Syndrome OR new ST-segment elevation/depression on EKG. (troponin release outside of ACS is allowed)
- 6) Fever >101.5°F
- 7) End stage HF: transplant list, ventricular assist device
- 8) Anemia requiring transfusion
- 9) Known interstitial lung disease
- 10) Suspected acute lung injury or acute respiratory distress syndrome (ARDS)
- 11) Pregnant or recently pregnant within the last 6 months
- 12) Severe valvular disease
- 13) Anuria
- 14) Allergy or hypersensitivity to nitroglycerin, furosemide or sulfa
- 15) Concern for cardiac tamponade or restrictive cardiomyopathy
- 16) Elevated intracranial pressure
- 17) Recent use of PDE5 inhibitors

It is important to note that AHF is a clinical diagnosis. In other words, there is no test or image that 100% conclusively demonstrates a patient does or does not have AHF. In most studies, 2 cardiologists who independently review the chart and agree its heart failure set the 'gold standard.' Thus, there will inevitably be instances where the ER will diagnose AHF and be wrong and vice-versa. From a clinical standpoint however, patients are cared for based on their presumptive diagnosis. Thus, instances where the ER diagnoses AHF and then the inpatient teams confirm an alternative diagnosis would NOT violate the spirit or actual intent of the study protocol.

5.3 STRATEGIES FOR RECRUITMENT AND RETENTION

Each site will have a lead PI and US Director, along with a dedicated study team. This study team, comprised of research assistants and coordinators, will perform both electronic screening (via tracking boards) and maintain a continuous physical presence in the ED to identify patients.. All patients with a final diagnosis of AHF at the time of hospital discharge will be considered to have AHF.

As we aim to design a pragmatic, ED-based study our inclusion/exclusion criteria are relatively broad compared to other therapeutic clinical trials.

Patients may be enrolled at anytime during their ED stay, but preferably within 3 hours of first placement in a room in the emergency department. Time spent in the waiting room will not count towards these 3 hours.

Screen Failures:

Patients who sign an informed consent but who are not randomized will be considered Screen Failures. Only data for randomized patients will be entered into the CRF. Serious adverse events should be reported for these patients from the time the ICF is signed through the time that the patient is declared a screen failure. One expected reason for screen failure will be the absence of > 15 B-lines at baseline.

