- That I will be responsible for maintaining each patient's consent form in the study file and provide each patient with a signed copy of the consent form.

Investigator Name and Title:

Institution Address:

Signature: _____

Date: _____

PROTOCOL SUMMARY

Title: *"Nitroglycerin vs. Furosemide using Lung Ultrasound Pilot Trial" (N-FURIOUS)*

[figure not shown]
Précis: Of the one million admissions for AHF in the US, approximately 80% are initially managed in the ED. Outcomes from AHF are poor: nearly 25% are dead or re-hospitalized within 30 days of discharge. The evidence base to treat AHF is limited. In fact, there are no pharmacologic therapies with Class I, Level A guideline recommendations. The acute

treatment of patients today is largely the same as 40 years ago. This proposal aims to build the evidence base for ED AHF care.

Using a two-site, randomized controlled design, this pilot study will test whether a nitrate intense strategy more effectively reduces congestion, defined by LUS B-lines, better than a diuretic intense strategy.

Objectives:	1: To determine whether a nitrate intense strategy safely reduces congestion, defined by LUS B-lines, better than a diuretic intense strategy. 2: To demonstrate feasibility of recruitment and compliance with study protocol to inform future study design and enrollment projections, an external site will also test our study protocol.
Endpoint	A comparison of total B-lines at the conclusion of ED AHF management or maximum of 6 hours after enrollment, whichever comes first.
Population:	Emergency department (ED) AHF patients. All patients who meet inclusion and no exclusion criteria will be enrolled during their ED visit within 3 hours of presentation.
Phase:	2
Number of Sites enrolling participants:	Two sites (3 total hospitals). Projected sample size, n=70.
Description of Study Agent:	Nitrate intense vs. Diuretic intense AHF treatment strategy
Study Duration:	2 years. There will be three months of start up, and one month of study conclusion work. Enrollment will occur over 20 months, which equals 3.5 patients month. As there will be staggered start up to determine replication, approximately 1-2 patients/month.
Participant Duration:	30 days post discharge

SCHEMATIC OF STUDY DESIGN

*whichever comes first

**Presentation is defined as first time recorded when placed in a room to be treated. This allows patients to still be enrolled despite a long waiting room time

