7.3.4 SCHEDULE OF EVENTS TABLE

Schedule of Events	Screening	Day 1 T00	Day 1 T02-04	Day 1 T06	Day 2-6 T24-D6	30 day follow up
Informed consent (I/E)	X					
Medical History	X					
Medication history	X					
Clinical Assessment#		X	X	X	X	
Body Weight, height, Vital Signs	ED SOC	VS only	VS only	VS only	BW/VS only	
5-point and 7-point Likert scale		X		X	X	
Labs: Electrolytes, hematology, NP, eGFR, Troponin	ED SOC					
12-lead ECG	ED SOC					
CXR	ED SOC					
LUS B-lines 8 zone	X (LUS T00)		X	X	X ^{^^}	
Nitrate vs. Diuretic intense management		X	X	X		
Lab draw: eGFR, Hgb/Hct [^]		X				
eCRF/data collection/verification		X				X
Assessment of AE/SAE's						X
Phone follow-up Vital Status						X

Subject payment		X				X
-----------------	--	---	--	--	--	---

SOC = standard of care, ED = Emergency Department, I/E = inclusion, exclusion, CV = cardiovascular, LUS = lung ultrasound, BW = body weight, NP = natriuretic peptide ^if collected as part of standard of care, will use that result. The last collected result will be used if not drawn on or close to discharge ^^ LUS to be performed up to 48 hours after hospitalization. If an obs unit patient, prior to discharge.

Further detail regarding timing of assessments: [NOTE: given clinical circumstances (i.e. left the ER for a test, discussion with consultant, etc) – the SITE PI has final discretion to continue to image a patient before or after the allotted window. This time MUST be recorded in the eCRF]

- T00: initial LUS scan (in ED for screening and eligibility)
- T02: 2-4 hours after initial treatment (in ED) (+/- 30 minutes)
- T06: 2-4 hours after T02 or pre-ED discharge, whichever comes first (+/- 60 minutes)
- T48: up to 48 hours after initial scan (Day 3) (+/- 12 hours)

** For vital signs during hospitalization. The nearest vital signs to the LUS exam will be captured.

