7.5 CONCOMITANT MEDICATIONS

All medications administered within 14 days prior to and during screening will be recorded in the case report form. Medications that are not specifically prohibited are permitted at the Investigator's discretion.

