10.5 SAMPLE SIZE OVERALL

This pilot study is powered to show a difference of at least 7 B-lines between treatment arms. With a total of 70 subjects (i.e. 35 in each arm), we will have 82% power to detect an effect size of 0.7 on the number of B-lines, where the type I error rate is controlled at 0.05 (two sided)..

Local Sample Size: As a multicenter study, the expected enrollment at IU is half the patients or 35. However, up to 50 patients may be enrolled depending on accrual rates at the other site.

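### The summary makes enrollment within 3 hours a requirement and the body makes it a preference; no prespecified comparison of the B-line count accounts for study drug given, or time elapsed, before randomization

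*Combined protocol and SAP*

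**What the plan says.** **Window.** The Population row of the Protocol Summary says that eligible patients "will be enrolled during their ED visit within 3 hours of presentation", and a note to the schematic counts presentation from room placement. Sections 5.3 and 7.3.1 start the clock at the same point but say: "Patients may be enrolled at anytime during their ED stay, but preferably within 3 hours of first placement in a room". The disagreement is therefore only about whether 3 hours is required or preferred.

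**Earlier treatment.** Sections 5.1 and 5.2 name some drugs (vasopressors, inotropes, PDE5 inhibitors) but set no limit on IV loop diuretic or nitrate before randomization. Section 7.6 prohibits nothing beyond the eligibility criteria. Section 2.3.1 describes both drug classes as current ED care. The treatment algorithm and the schematic are figures that could not be read, so a limit stated only there cannot be ruled out.

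**Recording and analysis.** Section 7.5 says: "All medications administered within 14 days prior to and during screening will be recorded in the case report form". Section 10.4.2 summarizes prior medications, and loop diuretic doses by arm. Section 10.4.3 lists baseline and in-hospital medications as possible covariates, which enter a logistic model with the treatment indicator if they are univariately significant. The primary endpoint (4.2.1) is the final B-line count.

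**Clocks.** T00 is the screening and eligibility scan (7.3.4). Protocol treatment runs for 6 hours from randomization (6.1.2).

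**The concern.** Under Sections 5.3 and 7.3.1 a patient can be randomized well into usual care, after receiving one or both of the drug classes that the trial compares. Two consequences are possible. B-line counts may vary more at the end because patients differ in what they received first, which costs precision. The arms may also be more alike in such patients, which would shrink the average difference. If drug is given between T00 and randomization, the T00 count no longer describes the patient at randomization.

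Section 3 says that the pilot is meant to inform a definitive trial. A small observed difference would be hard to interpret if the analysis could not show whether earlier treatment or late entry had contributed. The unsettled window adds a practical difficulty: the same late entrant fits the body of the protocol and does not fit its summary.

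**Working it through.** **Inputs from Section 10.5.** "This pilot study is powered to show a difference of at least 7 B-lines between treatment arms"; "we will have 82% power to detect an effect size of 0.7 on the number of B-lines"; 35 patients per arm; two-sided alpha 0.05. The SD is not stated. It follows as 7 / 0.7 = 10 lines.

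**Reproducing the plan's figure.** For a two-sample t test with n = 35 per arm, df = 2 × 35 − 2 = 68 and the noncentrality is d × √(n/2) = 0.7 × √17.5 = 2.93. Power is 82.3%, which matches the stated 82%. The normal approximation gives 83.4%. The smallest n reaching 82% by the t calculation is 35 per arm, so the sample size holds no reserve.

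**Margin.** Power is 80% at d = 0.679, a difference of about 6.8 lines, or 97% of the planned 7. It is 50% at d = 0.475, about 4.75 lines.

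**Dilution.** Suppose a share f of patients keeps only a fraction r of the arm difference. The average difference is 7 × [1 − f × (1 − r)]. For f = 30% and r = 0.5 this is 7 × 0.85 = 5.95 lines, so d = 0.595. The documents give neither f nor r, so both are assumed.

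| Share affected (f) | Keep 75%: difference, power, total N for 82% | Keep 50%: difference, power, total N for 82% |
|---|---|---|
| 0% | 7.00, 82.3%, 70 | 7.00, 82.3%, 70 |
| 10% | 6.825, 80.4%, 74 | 6.65, 78.3%, 78 |
| 20% | 6.65, 78.3%, 78 | 6.30, 73.8%, 86 |
| 30% | 6.475, 76.1%, 82 | 5.95, 68.9%, 96 |
| 50% | 6.125, 71.4%, 92 | 5.25, 58.1%, 122 |

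Allowing for the extra variance of a mixed population changes little (57.5% rather than 58.1% in the last cell). If affected patients kept none of the effect, power would be 73.8% at f = 10% and 30.3% at f = 50%. Nothing in the documents says where in this range the trial would fall.

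**What covariates can do.** If covariates have correlation ρ with the final count, the standardized difference becomes d / √(1 − ρ²). With ρ assumed to be 0.3, 0.5 or 0.7, and ignoring the small loss of degrees of freedom, undiluted power is 85.7%, 91.5% or 98.1%. In the case f = 30%, r = 0.5 it is 73.0%, 80.9% or 93.0%. The estimated difference in that case stays at 5.95 lines: precision improves, but the lost contrast does not return.

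**The case against.** The case on the other side is substantial, and several stronger readings fail against it.

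- A reader might infer that late entrants do dilute the contrast. The documents do not show this. Treatment runs 6 hours from randomization, so late entry alone does not shorten it, although leaving the ED can bring the last scan forward (7.3.4). Entry needs more than 15 B-lines (5.1), which screens out some patients who are already decongested. Staff keep a continuous ED presence (5.3), which favors early entry.
- A reader might infer that the plan makes no adjustment at all. It does list baseline medications as candidate covariates beside treatment. What stands is narrower: the route is data-driven, models a binary outcome rather than the count, and does not name pre-randomization IV treatment or time to randomization.
- A reader might infer that a patient randomized at 5 hours is a protocol violation under the summary. Sections 12 and 14.3 tie violations to the inclusion and exclusion criteria, the primary objective variable and GCP, and the window is in neither eligibility list. The wording still needs reconciling.
- A reader might infer that the T00 count undermines the primary result. The endpoint is the final count, so T00 matters for relative change and as a covariate. Section 17.3 places Scan 0 at enrollment, and no text describes treatment in the gap.
- Broad, pragmatic entry is a declared choice (5.3). That is fair, and the changes below are compatible with it.

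Late entry and earlier treatment are also separate matters: IV drug can be given inside 3 hours, so a strict window alone would not remove the problem.

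**Conclusion.** Two points hold on the text. The summary and the body disagree on whether 3 hours binds. No prespecified comparison of the B-line count takes account of study drug given before randomization or of time to randomization, and the readable text does not restrict such treatment.

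A reader might go further and infer bias between the arms. That is not supported, because randomization balances earlier treatment and entry time on average. The concern is lost precision and possible lost contrast.

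Its size is unknown. The range of about 80% to 58% power, against a reproduced 82.3%, rests on assumed shares of 10% to 50% and assumed retained effects of 75% to 50%, together with the implied SD of 10. The firm part is that the design has almost no power to spare, and that the plan as written could not show whether dilution had occurred. The change is worth making because it is cheap and mostly uses data that the plan already collects.

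**What to change.** 1. Reconcile the Protocol Summary with Sections 5.3 and 7.3.1 so that one window governs. The steps below apply whichever is kept.
2. Record the time from room placement to randomization.
3. Flag any IV loop diuretic or nitrate given before randomization, and whether it came before or after T00. Section 7.5 already captures medications through screening; the flag should run up to randomization.
4. In Section 10.4.3, prespecify a between-arm model for the final B-line count with baseline B-lines and pre-randomization IV diuretic or nitrate (yes/no) as named covariates, in place of univariate screening.
5. Add a sensitivity analysis limited to patients randomized within 3 hours of room placement.

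**Limits.** The covariates improve precision and do not recover a diluted effect. The sensitivity analysis addresses late entry, not drug given inside 3 hours.

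**Cost.** Protocol wording, two CRF fields, one or two degrees of freedom, and a smaller sample in the sensitivity analysis.

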5.4 PARTICIPANT WITHDRAWAL OR TERMINATION

5.4.1 REASONS FOR WITHDRAWAL OR TERMINATION

In accordance with the guiding principles of the Declaration of Helsinki, any patient is free to withdraw from participating in this study at any time and for whatever reason, specified or unspecified, and without prejudice. Investigators should attempt to determine the cause of withdrawal and, if desired by the patient, to make it possible for the patient to continue to participate in the study. The extent of a patient's withdrawal from the study (i.e. withdrawal from further study treatment, withdrawal from any further contact, etc.) should be documented. Every effort should be taken to follow all randomized patients, to the extent that the patient will allow, for the full follow-up period.

Investigators may discontinue study treatment for any other reasons concerning the health or well-being of the patient.

The reason for and date of study discontinuation and the reason for and date of withdrawal from the study must be recorded on the CRF. If study is discontinued because of an adverse event or a clinically significant abnormal laboratory test result, evaluations will continue until the event has resolved or stabilized or until a determination of a cause unrelated to the study procedure is made. The specific event or laboratory finding(s) must be documented. All evaluations should be performed, according to the protocol.

5.4.2 HANDLING OF PARTICIPANT WITHDRAWALS OR TERMINATION

The Full Analysis Set (FAS) will include all randomized patients. In accordance with the intent-to-treat principle, patients will be analyzed by the group to which they were randomized. Misrandomized patients (patients randomized in error who did not receive any study intervention) will be excluded. Analyses in the FAS will constitute the main efficacy results for the primary and secondary study efficacy endpoints.

The Per Protocol Set (PPS) will be a subset of the FAS and will exclude patients with major protocol violations. The major protocol violations that will result in exclusion from the PPS will be identified prior to unblinding the treatment assignments for final analysis. Patients will be analyzed in the treatment group to which they were randomized. Results of analyses in this analysis population will support the primary efficacy analyses in the FAS.

6 STUDY AGENT

[figure not shown]
6.1 STUDY AGENT(S) AND CONTROL DESCRIPTION

This study will test a nitrate intense vs. diuretic intense early AHF strategy. No investigational therapies will be used. No drugs or therapies that are not approved by the FDA will be allowed.

6.1.1 DOSING & DOSE ESCALATION

The algorithm below

outlines the treatment protocol.

[^]the protocol was designed to be an ED based protocol. Thus, for patients who leave the ER prior to 6 hours, deviations from the algorithm will NOT be protocol violations.

** ALL enrolled patients will be re-assessed at least twice during their ED stay, unless the patient is discharged from the ER or other clinical priority. First re-assessment will occur within 2-4 hours of first TREATMENT. Assessments outside this window are NOT allowed for study purposes unless at the discretion of the investigator. The second re-assessment will occur EITHER 2-4 hours after the first OR prior to discharge from the ER or at 6 hours after start of treatment. IF the pre-discharge assessment is missed in the ER, if possible, this should occur ASAP after arrival to the hospital floor, unless completed within one hour of the last assessment.

NOTE: the maximum dose allowed at any one time of IV Lasix is 200mg IV.

NOTE: For additional IV loop diuretic doses, the options under Restart Algorithm are three options. Clinical/Research team may choose one of the three loop diuretic dose options.

NOTE: The protocol is not optional by the clinical team. Of course, patient safety comes first, similar to all other interventional trials. However, similar to other interventional studies, once randomized, the study protocol should continue forward.

NOTE: Urine output: An estimated urine output is acceptable.

6.1.2 DURATION OF THERAPY

Both arms will continue until 6 hours after randomization. 6 hours was chosen to avoid confounding by patients with overly long ED LOS. At minimum, patients should receive at least one round of treatment. The protocol continues even if patients reach the floor. However, if in the opinion of the investigator, the protocol should not be continued once on the hospital floor, this is allowed and should be marked on the case report.

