3 OBJECTIVES AND PURPOSE

Objectives:

1: To determine whether a nitrate intense strategy safely reduces congestion, defined by LUS B-lines, better than a diuretic intense strategy.

2. To demonstrate feasibility of recruitment and compliance with study protocol to inform future study design and enrollment projections, an external site will also test our study protocol.

Purpose:

This pilot trial is designed to provide the necessary and sufficient information for a larger, definitive trial.

Hypothesis 1a: Nitrate intense treated patients will have less congestion, defined by LUS B-lines, than diuretic intense patients at 6 hours after start of treatment.

Hypothesis 1b: Nitrate intense treated patients will have greater dyspnea relief than diuretic intense patients at 6 hours after start of treatment.

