4 STUDY DESIGN AND ENDPOINTS

4.1 DESCRIPTION OF THE STUDY DESIGN

A two-site, prospective, randomized, pilot trial comparing a nitrate intense vs. diuretic intense strategy. All potential ED patients will receive an initial LUS scan. Performing LUS is within the standard of care and will be done at no cost to patients. It is not frequently used however, either for diagnosis, prognosis, or to guide clinical therapy. However, treating clinicians will be blinded to these results. If clinicians choose to perform their own LUS, those patients will not be excluded. Patients who provide written informed consent and meet all inclusion and no exclusion criteria will be randomized 1:1 to either study arm. For randomized patients, study protocol will continue until there is a decrease in B-

lines to ≤ 15 or 6 hours of care has been delivered. Subjects who are hospitalized prior to the completion of the 6 hour protocol may continue on the protocol until the six hour treatment window is concluded. All images will be stored and overread by an independent, expert ultrasonographer blinded to treatment arm.

Safety of patients are paramount. If a potential life threatening etiology is identified, the clinical team will be made aware immediately, irrespective of randomization arm. These occurrences will be recorded in the eCRF. While this will be a rare event, we will a priori establish that an additional patient will be accrued into the study and an additional modified intent to treat population for analysis will be performed, excluding these patients where a life-threatening etiology was identified (i.e. pericardial tamponade).

For patients who do NOT meet eligibility criteria, the results of their LUS will be provided to the clinical team as requested.

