4.2.1 PRIMARY ENDPOINT

The total number of B-lines at the conclusion of ED AHF management

Main Secondary Endpoints:

Dyspnea will also be assessed using a 5-point and 7-point Likert scale.

B-lines ≤ 15 at the conclusion of ED AHF management

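### Sections 4.1 and 6.1.2 disagree on when protocol treatment ends for a patient who reaches 15 or fewer B-lines early, and the time of the primary B-line count is not fixed

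*Combined protocol and SAP*

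**What the plan says.** **When protocol treatment ends.** Section 4.1 has one sentence, split by a page break: "study protocol will continue until there is a decrease in B" and then "lines to ≤ 15 or 6 hours of care has been delivered". Section 6.1.2 says "Both arms will continue until 6 hours after randomization". The only early end that 6.1.2 names is the investigator's judgment once the patient is on the floor.

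**When the primary count is read.** Section 4.2.1 defines the endpoint as "The total number of B-lines at the conclusion of ED AHF management". The Protocol Summary has "A comparison of total B-lines at the conclusion of ED AHF management or maximum of 6 hours after enrollment, whichever comes first". Hypothesis 1a (Sections 3 and 10.2) expects less congestion on nitrates "than diuretic intense patients at 6 hours after start of treatment".

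**When scans are done.** Section 6.1.1 asks for at least two re-assessments in the ED and places the second "EITHER 2-4 hours after the first OR prior to discharge from the ER or at 6 hours after start of treatment". Sections 7.3.4 and 17.3 time T02 at 2-4 hours after initial treatment (±30 minutes) and T06 at 2-4 hours after T02 or before ED discharge, whichever is first (±60 minutes). None of these scan rules mentions the 15-line threshold.

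**The concern.** The possible stopping trigger and the primary outcome are the same measurement. Under 4.1 the arm that clears B-lines faster would have protocol treatment ended more often. If that stop also counted as the end of ED management, the faster responders would be scored earlier, at a value just under the common threshold. Under 6.1.2 alone, neither exposure nor scan time would depend on B-line response.

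Sites could therefore follow the document and still differ in the treatment they deliver and in the scan they score. The trial is unblinded (10.6.1), so masking gives no protection. It is also unclear whether stopping, or not stopping, at 15 or fewer is a major violation for the per-protocol set (10.3). Section 3 says the pilot is to inform a definitive trial, so its effect estimate needs a single meaning.

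**Working it through.** **1. The rules side by side**

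| Section | Event | Rule | 6-hour clock starts at |
|---|---|---|---|
| 4.1 | Protocol ends | B-lines 15 or fewer, or 6 h | care delivered |
| 6.1.2 | Both arms end | 6 h, no B-line stop | randomization |
| Protocol Summary | Primary count | End of ED management, at most 6 h | enrollment |
| 4.2.1 | Primary count | End of ED management | none |
| 3 and 10.2 | Primary count | 6 h | start of treatment |
| 6.1.1 | Second scan | Three alternatives, one at 6 h | start of treatment |

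There are two end-of-treatment rules, three statements of the endpoint time and four clock origins. No section defines the end of ED management.

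**2. How far T06 can move**

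- Nominal: 2 + 2 = 4 h to 4 + 4 = 8 h after treatment.
- With both tolerances: (2 − 0.5) + (2 − 1) = 2.5 h to (4 + 0.5) + (4 + 1) = 9.5 h.
- Earlier still if the patient leaves the ED.

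**3. The plan's power (10.5)**

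Inputs: 35 per arm, 7 B-lines, effect size 0.7, two-sided 0.05. Implied SD = 7/0.7 = 10. Noncentrality = 0.7 × √(35/2) = 2.93. The two-sample t-test on 68 degrees of freedom gives 82.3%, which reproduces the stated 82%. The sample size is not in dispute here.

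**4. What scoring the threshold scan would do (all inputs assumed)**

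The documents give no baseline mean, rate of decline or spread of response. In both sets below, scans fall at 3 h and 6 h, counts are floored at zero, and a patient at 15 or fewer at 3 h is scored there.

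*Set A.* Baseline SD 12, truncated above 15; mean declines of 2.83 and 4.0 lines/h, SD 1.5; reading SD 2. Losses are computed before rounding.

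| Baseline mean (before truncation) | Difference, all at 6 h | Difference, early scan scored | Loss |
|---|---|---|---|
| 30 | 5.6 | 4.7 | 16% |
| 35 | 6.1 | 5.3 | 12% |
| 45 | 6.7 | 6.4 | 5% |

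At mean 30, 34% of the faster arm and 23% of the slower arm stop early. The SD also narrows, from about 11.6 to 10.1, so the standardized effect moves only from 5.6/11.6 = 0.48 to 4.7/10.1 = 0.47. Power at 35 per arm goes from 51% to 49%. At means 35 and 45 it starts at 49-50% and moves by no more than 2 points. These levels are below 82% because the assumed spread is wider than the plan's implied SD of 10, so only the change is informative.

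*Set B.* Baseline SD 8; mean 6-hour fall of 5, 10 or 15 lines on diuretic and 7 more on nitrate, SD 6; reading SD 3.

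| Baseline mean | Difference, all at 6 h | Difference, early scan scored | Power |
|---|---|---|---|
| 25 | 5.3-6.7 | 3.8-5.5 | 77-83% to 67-77% |
| 35 | 6.6-6.9 | 5.8-6.7 | 79% to 77-78% |
| 45 | 7.0 | 6.8-7.0 | almost unchanged |

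Case by case at mean 25, power falls from 83% to 77%, 82% to 73% and 77% to 67%, that is by 6, 9 and 10 points.

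**The case against.** The strongest reply is that no sentence moves the primary scan to the moment the threshold is met. Section 4.1 ends the study protocol, whereas 4.2.1 speaks of ED management, and a patient at 15 or fewer may still be under ED care. Section 6.1.1 requires two re-assessments of every enrolled patient, with exceptions for discharge and clinical priority but none for response. Hypothesis 1a points to 6 hours. This stands: a reader might infer that 4.1 makes the threshold scan the primary value, but that holds only if the undefined end of management is taken to include the 4.1 stop.

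A reader might also carry the raw loss of up to 16% straight into lost power. With the SD held at 10, a 10% or 20% smaller difference would cut power to 73.8% or 63.7%. That overstates the harm, because scoring patients near a common threshold narrows the spread too.

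Finally, the treatment algorithm and schematic are figures that are not reproduced, and they may state the rule that sites actually follow. They could not make both 4.1 and 6.1.2 correct.

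**Conclusion.** The conflict between 4.1 and 6.1.2 is real in the current text and must be reconciled; no position is taken here on which treatment rule is right. The time of the primary count is separately inconsistent in its definition and its clock. Response-dependent scan timing is a conditional consequence, not something the documents state.

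If it occurred, the raw difference would be biased toward zero. The size rests wholly on assumed inputs: power falls by about 0 to 3 points in Set A, and in Set B by 6 to 10 points at a baseline mean of 25, 1 to 2 at 35 and essentially none at 45. The main harm is an effect estimate whose meaning depends on the section a site follows. The documents do not support a claim that the trial is materially underpowered for this reason.

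**What to change.** 1. Replace the statements in 4.1 and 6.1.2 with one statement of when protocol treatment ends, match the algorithm figure to it, and say how departures from it count for the per-protocol set.
2. Separately, define the primary B-line value for every randomized patient as the second re-assessment scan, with one clock origin, a target time and a window, whenever protocol treatment stopped. Six hours after start of treatment, as in Hypothesis 1a, is one option. Use the same wording in the Protocol Summary, 4.2.1, 10.2 and 10.4.3, and the same scan for the secondary endpoint of 15 or fewer B-lines.
3. Do not simply name T06. As scheduled it can fall 4-8 hours after treatment before tolerances, or earlier at ED discharge, so its window in 7.3.4 and 17.3 has to change as well.
4. State which value is used, or that it is missing, for patients who leave the ED before the window. Those discharged home cannot be rescanned, since 7.3.3 allows no in-person visit after discharge.

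The cost is small: wording, a tighter window for a scan already scheduled, and some scans on the floor, which 6.1.1 already allows when the ED assessment is missed.
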